- We have selected only one IOP group per site to participate in the study. We decided on this approach as some sites only have one IOP group, but it does potentially limit our sample size. However, as noted in the Power Analysis section (Section C.7), we have sufficient power even with a smaller sample size as we have increased power with both the number of sites and number of steps. We will select the most stable and strongest group at each site. While this can lead to selection bias, we believe it will increase internal validity to have as strong a PARS condition as possible with a maximally motivated and stable staff. In the first controlled trial, it is important that PARS be as strong as possible to prevent abandoning a potentially effective program. Future research can determine the range of clinician motivation and skill associated with effective PARS administration.
- Our outcome assessment instruments are all brief. While this is a limitation, we have selected psychometrically strong measures *and collect clinician collateral data*. And with a sample of 900 participants, it is critical to collect as much data as possible using text message and online surveys, which require brief measures. Finally, to minimize attrition it will be critical to minimize the assessment burden.
- For our information, attitude, and help-seeking measures, we have selected the measures developed for the R21 study rather than existing measures. After a detailed review of the literature, many measures were found to be very long and repetitive, contain outdated suicide information, or both. The measures included in this study were selected because they are based on existing measures, have accurate items, show strong internal consistency in pilot work, have content validity with PARS curriculum, and are brief.
- One possible limitation to our outcome assessment protocol is the potential priming of effect by repeated assessment. However, we believe the precision will be increased and repeated assessment is necessary for mediation and dose analyses. The effect will be equated between conditions through randomization.

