Key notes regarding study setting and design: Four community substance abuse treatment agencies have partnered with the research team for this study. These four agencies have 1-9 sites each that are scattered around Western Washington for a total 15 sites. Each site varies from 1-3 Intensive Outpatient Program (IOP) groups which run simultaneously. Each IOP has approximately 24-36 sessions of 2-3 hours each (72 hours total). Once they complete all sessions, the IOP restarts. New IOP clients enter the program at any time and stay till they have attended all 24 or 36 sessions. Thus, each Step in this Stepped Wedge design will be an entirely new set of clients.

Only one IOP for each site will be selected to be the focus of this study (Selected IOP). All client participants will be recruited and consented by research staff and the interventions (TAU vs. PARS) will be in the Selected IOP.

Within each Step, data collection will be as follows. Two weeks prior to the week Standard/PARS session is to be conducted in the selected IOP, research staff will connect with counselors at that site to (a) set up a plan for client recruitment and (b) have counselors complete online assessments themselves. One week prior to the Standard/PARS session, the research staff will come to the program 1-3x to recruit participants with the goal of recruiting all willing participants enrolled in that Selected IOP. Baseline assessments completed at recruitment. Follow-up assessments online or by phone two weeks, then one, three, and six months after recruitment.

Administrative Supplement: We will conduct a sub-study to culturally tailor PARS for use in Alaska Native and American Indian (ANAI) communities. This will be conducted in three ANAI communities with whom [name] and/or [name] are currently collaborating.

1.7 Intent. Check all the descriptors that apply to your activity. You must place an "X" in at least one box.

This question is essential for ensuring that your application is correctly reviewed. Please read each option carefully.

Descriptor
 1. Class project or other activity whose purpose is to provide an educational experience for the researcher (for example, to learn about the process or methods of doing research).
 2. Part of an institution, organization, or program's own internal operational monitoring.
 3. Improve the quality of service provided by a specific institution, organization, or program.

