All IOP counselors will be trained in the Step where they are randomized to implement PARS. In this way, the study sites are “engaged” in the research as counselors on site will provide the study interventions. The agencies will be deferring human subjects review to the UW and have completed an Institutional Agreement for IRB Review (IAIR) with each site.

[name], who developed PARS, will provide all the training. To maximize the value to our community partners and assure a counselor trained in PARS is available on the day the PARS module is scheduled, all consenting counselors will be offered the opportunity to participate in the training so that someone can substitute if the designated PARS counselor is unavailable.

PARS counselor adherence will be evaluated at the first PARS administration by having an adherence coder sit in on the PARS session. Observation is the method requested by the agency treatment partners as least disruptive and most acceptable to clients. As adherence coders will have participant contact and be hearing the treatment session, they will complete any training on specific agency procedures regarding treatment observers with regard to client PHI so the adherence coders meet all agency standards. No client PHI will be collected as part of adherence coding – the focus is on the counselor’s level of adherence to PARS and not client identity nor comments.

Both Conditions:

Any additional treatments outside of the IOP program (e.g., mental health-oriented counseling, pharmacotherapy) will be available during all phases of the Stepped design. Washington State mandates self-help group attendance in addition to attendance of group and individual IOP sessions; this will also remain consistent throughout each site’s participation (regardless of when PARS is implemented at each site).

Client Participant Assessment Procedures:

Reminder – clinics are randomized at the clinic level. Clients and counselors have no choice in if they receive the intervention. This randomization effects clients and counselors regardless of whether they are study participants or not. As noted above, participants are informed about this in the consent form and we request waiver of consent for the non-participants.

Baseline Assessment

Will always occur one week prior to session intervention.

Will be conducted by in-person group administration. Assessments will be completed on paper or tablet computers. Expected to take 15-30 minutes.

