If the individual does not have time or requests an individual assessment, this will be offered at a later time or in a different room at the same time.

Post-Intervention Assessment

Will be conducted one week after the PARS or TAU group session (i.e., 2 weeks after baseline). Assessments will be completed using online assessment. Participant will receive a text message or email (their preference) with a link to the assessment. If a participant prefers, follow-up assessments can be conducted by phone in which case research staff will call participant when the assessment is due. Expected to take 5-10 minutes.

Long-Term Follow-Up Assessments

Will be conducted 1, 3, and 6 months after the baseline assessment. Participants will receive a text message or email (their preference) with a link to the assessment. If a participant prefers, follow-up assessments can be conducted by phone in which case research staff will call participant when the assessment is due. Expected to take 10-15 minutes.

Following their completion of the 6-month assessment, participants have the option of checking a box—or verbally agreeing if the survey is conducted via phone—at the end of the survey to request the correct answers to the PARS Suicide Knowledge Scale questions (description of measure in Section 5.13 of current protocol). We will not provide the participant's individual survey responses during this process.

Counselor Participant Assessment Procedures:

Baseline Assessment

Will be conducted by in-person group administration. Assessments will be completed on tablet computers or paper versions. Expected to take 10-20 minutes.

If the individual does not have time or requests an individual assessment, this will be offered at a later time or in a different room at the same time.

Additionally, at the beginning of each Step, the Research Coordinator (or site-assigned RA) will reach out to the Site Administrator and Treatment Coordinator to ask if any new clinical staff have joined (or left) the site since the last Step. To clarify who was there previously, the Research Coordinator will provide a list of counselors who have been approached (regardless of whether they completed or refused).

Post-Training and Post-Intervention Follow-Up Assessment

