Will be conducted immediately after the PARS training (when this is scheduled according to the Stepped wedge design) and immediately after the first administration of PARS, only for the counselor leading the PARS session. Assessments will be completed using online assessment using a tablet computer or paper version. Expected to take 5-10 minutes.

Ongoing Follow-Up Assessments

Will be conducted every 4 months (i.e., at each Step in the Stepped wedge) and one at the end of the study (after Step 6). Participants will receive a text message or email (their preference) with a link to the assessment. If a participant prefers, follow-up assessments can be conducted by phone in which case research staff will call participant when the assessment is due. Expected to take 10-15 minutes. (NOTE: for Step 1, counselors consented to 6 assessments and they were every 6 months. They also did not consent to the assessment at the end of the study. The PARS counselor Step 1 Re-Consent IRB ver-1 8-

21-17 document clarifies the questions to be asked at the Step 2 follow-up to re-consent these counselor participants. Also noted in Section 8.)

Study Locations

Location	Activities
Harborview Pat Steel Building	Study management, data management, entry, and analysis
Evergreen Recovery	Main Agency
Everett Outpatient	Recruitment, baseline assessment, study intervention
Lynnwood Outpatient	Recruitment, baseline assessment, study intervention
Lakeside Milam Recovery Center	Main Agency
Auburn	Recruitment, baseline assessment, study intervention
Edmonds	Recruitment, baseline assessment, study intervention
Everett	Recruitment, baseline assessment, study intervention
Issaquah	Recruitment, baseline assessment, study intervention
Kirkland	Recruitment, baseline assessment, study intervention
Puyallup	Recruitment, baseline assessment, study intervention
Renton	Recruitment, baseline assessment, study intervention
Seattle	Recruitment, baseline assessment, study intervention
Tacoma	Recruitment, baseline assessment, study intervention
Northwest Integrated Health	Main Agency
Tacoma	Recruitment, baseline assessment, study intervention
Puyallup	Recruitment, baseline assessment, study intervention
Lakewood	Recruitment, baseline assessment, study intervention
Olalla Recovery Centers	Main Agency
Gig Harbor	Recruitment, baseline assessment, study intervention

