Participants will be contacted by text message (using Twilio within the REDCap system) or email (their preference) with a link to the online REDCap survey unless they request contact by phone to do a phone interview. If they do not complete the survey when expected, research staff will contact them to remind them, solve any technical difficulties, or complete the assessment by phone. Using the follow-up locating consent form and associated contact information form (attached), research staff will reach out through the means they approve to locate them for follow-up interviews. This includes phone, email, texts, letters, private messages to social media, or contacting a friend or treatment provider they authorized us to speak to. (As noted in 8.2b below, we separate the follow-up locating consent from the main consent so that we can show it to people providing contact information to assure them we have the participant's permission without sharing any details about the study.)

5.11 Future contact with subjects. Do you plan to retain any contact information you obtain for your subjects so that they can be contacted in the future?

	No
	Yes

→ If yes, describe the purpose of the future contact, and whether use of the contact information will be limited to your team; if not, describe who else could be provided with the contact information. Describe your criteria for approving requests for the information.

Examples: inform subjects about other studies; ask subjects for additional information or medical record access that is not currently part of the study proposed in this application; obtain another sample.

Client participants opted in/out of the following statement at the time of consent: "It is possible that, depending on the results of the study, the research team may want to interview you again in the future. Please initial here _____ if you are willing to be contacted in the future about participation in a follow-up study. You are not required to participate in further research if contacted in the future." No such study, nor contact with participants, will be performed without explicit review and approval by UW HSD. Only the research team will have this information. It will not be shared.

5.12 Alternatives to participation. Are there any alternative procedures or treatments that might be advantageous to the subjects?

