PARS Acceptability. Addictions counselors will complete the PARS Counselor Acceptability Scale,¹ a 13-item survey that was developed in our R21 trial to measure acceptability, ease, and perceived effectiveness of incorporating PARS into day-to-day IOP procedures where it had excellent internal consistency ($\alpha = .99$).

C.6. Procedures

Baseline Assessment will be conducted by in-person group administration as described in Recruitment above. If the individual does not have time or requests an individual assessment, this will be offered at a later time or in a different room at the same time. Assessments will be completed on tablet computers.

Post-Intervention Assessment will be conducted after the PARS or TAU group session and include just the information and attitudes items as too little time has passed for other behavioral measures to be relevant.

Follow-Up Assessments will be conducted 1, 3, and 6 months after baseline assessment. Assessments will be completed using online assessments using their smart phone, text message responses, or a computer. If a participant prefers or has any technical problems, follow-up assessments can be conducted by phone. [name] current trials use these modalities to complete questionnaire follow-up assessments with over 500 Soldiers and Marines. Online methods are extremely effective with a very mobile population such as Service Members who move while active duty and as they separate from the military and also for those in addiction treatment who are often moving residences or homeless.

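### Month-1 help-seeking asks about the past month but is timed from baseline, a week before the session, so up to about 7 pre-session days can dilute the effect on which the trial is powered

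*SAP*

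**What the plan says.** - **Baseline to session.** Protocol 5.1 says of the baseline assessment: "Will always occur one week prior to session intervention". SAP C3 (Stepped Wedge Design) also puts baseline in the week before the selected session. Protocol 5.1 confirms the gap through the post-intervention survey: "Will be conducted one week after the PARS or TAU group session (i.e., 2 weeks after baseline").
- **Timing of follow-up.** SAP C.6: "Follow-Up Assessments will be conducted 1, 3, and 6 months after baseline assessment". Protocol 5.1: "Will be conducted 1, 3, and 6 months after the baseline assessment". Protocol 1.6 counts from enrolment instead: "then one, three, and six months after recruitment". Neither document counts from the session.
- **Recall period.** The help-seeking items ask about the past month (SAP C.5 Measures; Protocol 5.13). The SAP states an adapted time frame only for the suicidality measure.
- **Assurance.** SAP C3 says that placing baseline just before the session makes follow-up cover the time after PARS.
- **Power.** SAP C.7 powers month-1 help-seeking only, at 15.6% against 28.1% from the pilot. It states 89% power at N=900 and 80% at N=675, and calls this conservative because the full longitudinal model also uses participants with incomplete follow-up.

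**The concern.** Counted from baseline, a month-1 survey falls about three weeks after the session, and a one-month recall period reaches back to about baseline. For a PARS client, help-seeking in the pre-session days cannot have been caused by PARS, so those days pull the PARS rate toward the TAU rate.

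SAP C.6 itself leaves behavioural measures out of the post-intervention survey because too little time has passed for them. The same reasoning applies, more weakly, to month 1.

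At stake is the size of the month-1 help-seeking difference, which is the only contrast behind the stated sample size. A diluted estimate could be taken for a weak intervention.

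Among the primary outcomes, only month-1 help-seeking is affected. Knowledge and attitudes have no recall window. The past-month windows at 3 and 6 months lie wholly after the session. Exploratory Aim 5 shares the overlap at month 1: substance use covers the past 30 days, the Protocol's ideation item covers the past month, and the SAP's suicidality window runs back to the previous assessment. That window may reach baseline, because the SAP's post-intervention survey carries only information and attitude items.

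**Working it through.** **Overlap.** Take baseline as day 0, the session as day 7 and the month-1 survey as day 30. A 30-day recall period then covers days 0 to 30: 7 days before the session and 23 after.

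**Inputs from SAP C.7 and C3.** Rates 0.156 and 0.281; 15 sites in five groups of three; 6 steps; 10 people per site per step (N=900) or 7.5 (N=675).

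**Assumptions, not in the documents.** Two-sided alpha 0.05; ICC 0.005; constant help-seeking rate within the pre-session and post-session periods; exact 30-day recall; pilot rates that describe full months before and after PARS.

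**Reproducing the SAP's figure.** The Hussey-Hughes variance is

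Var = I·s²(s² + T·τ²) / [(IU − W)s² + (U² + ITU − TW − IV)τ²]

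Here I=15, T=6, U=45, W=495 and V=165.

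- IU − W = 675 − 495 = 180.
- U² + ITU − TW − IV = 2025 + 4050 − 2970 − 2475 = 630.
- Average binomial variance: (0.156×0.844 + 0.281×0.719)/2 = 0.16685.
- With n=10: s² = 0.016685 and τ² = (0.005/0.995)×0.16685 = 0.000838.
- Var = 15×0.016685×(0.016685 + 6×0.000838) / (180×0.016685 + 630×0.000838) = 0.001539, so SE = 0.0392.
- Power = Φ(0.125/0.0392 − 1.96) = 89.0%.
- With n=7.5: SE = 0.0448 and power = 79.7%.

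Both stated figures are reproduced. An ICC of 0.005 fits them but is not the only value that would.

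**Adding d pre-session days.** The monthly hazards are −ln(0.844) = 0.1696 before the session and −ln(0.719) = 0.3299 after it. The PARS rate at month 1 is

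p = 1 − exp{−[(d/30)×0.1696 + ((30 − d)/30)×0.3299]}

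| Pre-session days | PARS rate | Difference (points) | Power, N=900 | Power, N=675 |
|---|---|---|---|---|
| 0 | 0.2810 | 12.5 | 89.0% | 79.7% |
| 3 | 0.2694 | 11.3 | 83.0% | 72.2% |
| 7 | 0.2536 | 9.8 | 71.8% | 60.3% |

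At 7 days the ratio of differences is 0.0976/0.125 = 0.78, a 22% reduction.

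**Sensitivity to the ICC, N=900, 0 to 7 days.** ICC 0: 91.8% to 76.1%. ICC 0.05: 79.1% to 59.7%. The loss is similar across this range.

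**Sensitivity to the dilution model.** If the effect is proportional to exposed days, the difference is 12.5×23/30 = 9.6 points. With a between-site coefficient of variation of 0.15, which also reproduces the stated figures (89.3% and 79.8%), power at 7 days is 71.0% and 59.2%.

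**The planned test.** SAP C.7 tests Treatment-by-Time terms in a model with baseline and months 1, 3 and 6. A linear version, with random site and participant effects, gives these approximate powers for the month-1 contrast, 0 to 7 days of overlap:

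| Within-person correlation (assumed) | N=900 | N=675 |
|---|---|---|
| 0 | 90% to 74% | 81% to 61% |
| 0.3 | 97% to 87% | 92% to 77% |
| 0.5 | 99.6% to 96% | 98% to 89% |

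**The case against.** The strongest reply is that the size of the loss depends on a source the reader cannot see. The SAP describes the pilot effect as the month after PARS against the month before (Specific Aims, C.1), but says only that pilot follow-up was at a 1-month time point. SAP C.7 also calls this trial's own baseline-anchored month 1 post-intervention, so that label settles nothing. If the pilot was timed from baseline too, similar dilution is already inside the 12.5 points and the correction largely disappears. This objection stands, and it makes the power figures conditional.

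The overlap may also be shorter than 7 days. Protocol 1.6 says "the research staff will come to the program 1-3x to recruit participants" in the week before the session, so some baselines may fall closer to it. Protocol 5.10 provides for chasing late surveys, and no completion window is stated for month 1. Help-seeking that comes soon after the session would also lessen the dilution.

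It is also fair to say that the 89% and 80% do not describe the planned test. The longitudinal contrast may start from higher power, and months 3 and 6 are untouched. But a larger model does not restore the month-1 difference, so the SAP's description of its power as conservative does not answer the point.

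A reader might infer three stronger things that the documents do not support:

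- **Bias in favour of PARS.** The timing is the same in both conditions, and the distortion runs toward no effect.
- **A mid-trial change of anchor is shown to be harmful or pointless.** Under the constant-rate assumption a TAU client's month-1 rate is the same under either anchor. Any such verdict would need a common shift that nothing in the documents establishes.
- **The mediation claim must rest on months 3 and 6.** Figure 2 is not shown, so the time point of the path concerned is unknown.

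**Conclusion.** The concern holds in limited form. The timing facts are in both documents: an on-schedule month-1 survey can include up to about 7 of 30 pre-session days, so the SAP C3 assurance is not met for this item at this visit.

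The consequence is dilution of the month-1 help-seeking contrast. Under the stated assumptions the SAP's power falls from 89%/80% to between 83%/72% (3 days) and 72%/60% (7 days). The planned contrast loses less when within-person correlation is positive. The loss could be close to nothing if surveys come in about a week late or if the pilot was itself timed from baseline.

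It would be wrong to conclude that the trial has 72% or 60% power. Those are the 7-day figures under assumed inputs, and the documents give no basis for choosing a point in the range. The matter deserves a small correction and does not threaten the trial's validity.

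**What to change.** **If client enrolment has not begun:** time the 1-, 3- and 6-month follow-ups from the date of the Standard or PARS session, in both conditions. The cost is an edit to the automated survey schedule, and follow-up ends about one week later per participant.

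**If enrolment has begun:** the Protocol suggests this, though it does not say so outright for clients. Section 5.1 notes that "for Step 1, counselors consented to 6 assessments and they were every 6 months", and section 5.11 reports that "Client participants opted in/out of the following statement at the time of consent". In that case keep the baseline anchor by default, so that survey timing does not change with calendar step in a stepped-wedge design. Then:

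- Correct the SAP C3 sentence to say that the month-1 recall period may include up to about a week before the session.
- Restate month-1 power in SAP C.7 as a range for 0 to 7 pre-session days, giving the alpha, ICC and within-person correlation used, and say whether the pilot month was counted from the session.
- Report the observed number of pre-session days in the month-1 window, by condition.
- At most, add a note to the mediation plan that the month-1 window may partly precede the session.

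These changes cost only text and one descriptive table. Session and survey dates are needed for each participant.
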